13.3 Recording and reporting of SAEs, SARs AND SUSARs

[figure not shown]
All serious adverse events that are trial or treatment related will be recorded and immediately reported to the Chief Investigator and within 1 working day (24 working hours) to the ExeCTU Trial Manager. If these are also classed as unexpected, they will be reported to the relevant ethics committees.

We will, in line with other complex intervention studies, monitor non-serious adverse events, serious adverse events that are not trial or treatment related, serious deterioration, and active withdrawals from treatment, with specific questions in the follow-up and in response to specific participant-initiated reports. Symptoms of depression or anxiety will not be defined as adverse events unless suicidal ideation, plans or an attempt has been made. The reporting period for all events and reactions will be from referral to 12weeks post baseline follow-up. Data on any adverse events will be collected by a member of the research team at each assessment and entered directly into the EDC.

The SAE form will capture the following data:

- Date and time of onset
- Date and time investigator became aware
- SAE category
 - o Death i.e. (homicide, suicide, accident, illness, all appropriate options) etc.)
 - Life threatening i.e. (suicide attempt, serious assault, self- harm)
 - o Hospitalisation or prolongation of existing hospitalisation or referral to crisis team
 - Persistent or significant disability or incapacity i.e. (include development of problematic substance/ alcohol abuse; onset of new Axis I disorder)
 - Congenital anomaly or birth defect
 - Other i.e. (potentially dependent life events, e.g. job loss divorce)
- The intensity will be specified as mild, moderate or severe
- The SAE will be determined as intermittent or continuous
- The SAE will be determined as expected or unexpected
- The SAE outcome will be determined as resolved with a date provided, resolved with sequelae, ongoing (follow ups to the SAE will be provided when there is a change to report in participants condition) or died (if died the cause of death will be specified)
- The SAE relationship to the study or trial procedures will be determined as not related, unlikely to be related, possibly related, definitely related or unknown
- A detailed description of the event will be provided and this field will also be used to
 document the dates and number of attempts made to contact a participant by phone and/or
 email in order to obtain details about the event, the discussion that took place during any
 successful phone calls/emails and subsequent actions agreed or discussed between the
 participant and researcher/clinician
- The CI will report on their assessment of the implications (if any) for the safety of study participants and how they will address the implications
- The form must be signed and dated by the CI

Figure 2 Safety reporting flow chart

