standardized measures or contacts initiated by the participant. If the researcher has serious concerns about a participant, where appropriate, after discussion with the clinician, the clinician will contact the participants (by email, telephone) to review the situation, provide guidance and offer to write a referral letter, subject to participant consent. These procedures will be made explicit in all information sheets. Any concerns detected this way will be recorded on a standardised pro forma, a copy which will be sent to the sponsor for the trial. The same process will be activated in response to any concerns raised by participants at other times, either spontaneously or in responses during the assessments. We will record both serious and non-serious adverse events as defined by the National Research Ethics Service (e.g. deaths; self-harm; serious violent incidents, referral to crisis care or admission to psychiatric hospital) within both groups and report them to the Research Ethics Committee to determine whether events are related to the treatments and to take appropriate action.

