13.2 Definitions

Standard definitions for adverse events etc are in the table below. Because the current interventions are digital self-help rather than a medicinal product and involve no biological agent, it is not appropriate to define adverse events etc re any untoward medical occurrence – rather as a psychological intervention, appropriate adverse events would include those related to mental state and behaviour:

- i) Serious adverse events (SAEs) including death, suicide attempt, self-harm, serious accident or violent incident, referral to crisis care or admission to psychiatric hospital.
- ii) Adverse Events (AE) may include significant worsening symptoms of anxiety, worsening symptoms of depression, as operationalized by a reliable deterioration of movement from 'mild' to 'severe' or 'moderate' to 'severe' levels of symptoms on GAD7 or PHQ9 AND a change of ≥4 points on GAD7 or ≥6 points on PHQ9 from baseline assessment to 6 weeks assessment or from 6 weeks assessment to 12 weeks assessment, new instance of self-harm, new instance of suicidality.

The following definitions are therefore adapted in light of this – see **Table 12**.

Table 12 Definitions of Events

Term	Definition
Adverse Event (AE)	Standard: Any untoward medical occurrence in a participant to whom a medicinal product has been administered, including occurrences which are not necessarily caused by or related to that product. Adapted: Any deterioration in mental state or behaviour in a participant to whom the intervention has been administered, including occurrences which are not necessarily caused by or related to the intervention.

Adverse Reaction (AR)

Standard: An untoward and unintended response in a participant to an investigational medicinal product which is related to any dose administered to that participant.

The phrase "response to an investigational medicinal product" means that a causal relationship between a trial medication and an AE is at least a reasonable possibility, i.e,. the relationship cannot be ruled out.

All cases judged by either the reporting medically qualified professional or the Sponsor as having a reasonable suspected causal relationship to the trial medication qualify as adverse reactions.

Adapted: An untoward and unintended response in a participant to an intervention which is related to any dose of the intervention administered to that participant.

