13.4 Responsibilities

Researchers at central site (University of Exeter) to check for SAEs, AEs and ARs when participants complete treatment or at follow-up, potentially in response to automated feedback from website.

Chief Investigator (CI) is responsible via liaison with research team at central site for:

- 1. Ensuring that all SAEs are recorded in EDC and reported to the ExeCTU Trial Manager within 24 working hours / 1 working day of becoming aware of the event and provide further follow-up information as soon as available.
- 2. Ensuring that SAEs are chased with ExeCTU Trial Manager if a record of receipt is not received within 2 working days of initial reporting.
- 3. Ensuring that AEs and ARs are recorded and reported to the ExeCTU Trial Manager in line with the requirements of the protocol.
- 4. Immediate review of all SUSARs.
- 5. Review of specific SAEs and SARs in accordance with the trial risk assessment and protocol as detailed in the Trial Monitoring Plan.

Sponsor (NB where relevant these can be delegated to CI and trial manager) is responsible for:

- 1. Central data monitoring and verification of AEs, ARs, SAEs, SARs and SUSARs according to the trial protocol within the database (EDC).
- 2. Reporting safety information to the CI, delegate or independent clinical reviewer for the ongoing assessment of the risk / benefit according to the Trial Monitoring Plan.
- 3. Reporting SAEs that are related to the trial and unexpected, by email to the research ethics committee.
- 4. Reporting SAEs that are related to the trial and unexpected, by email to the research ethics committee.
- 5. Reporting safety information to the independent oversight committees identified for the trial (Data Monitoring Ethics Committee (DMEC) and / or Trial Steering Committee (TSC)) according to the Trial Monitoring Plan.
- 6. Expedited reporting of SUSARs to the Competent Authority (MHRA in UK) and REC within required timelines.
- 7. Notifying Investigators of SUSARs that occur within the trial.
- 8. Preparing standard tables and other relevant information in collaboration with the CI and ensuring timely submission to the MHRA and REC.

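### The SAE rules in sections 13.1 to 13.4 contradict each other, so the timing, route and class of a reported SAE depend on which section staff follow

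*Protocol*

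**What the plan says.** **Section 13.3, first paragraph.** "All serious adverse events that are trial or treatment related will be recorded and immediately reported to the Chief Investigator", and to the Trial Manager "within 1 working day (24 working hours"). Those that are also unexpected go to the ethics committees.

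**Section 13.3, second paragraph.** The trial will monitor "serious adverse events that are not trial or treatment related, serious deterioration, and active withdrawals from treatment, with specific questions in the follow-up" and through reports that participants make themselves. No deadline is attached. The paragraph adds: "Data on any adverse events will be collected by a member of the research team at each assessment and entered directly into the EDC". Next comes a description of the form for SAEs, which grades relatedness on a scale that starts at not related and includes unknown.

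**Section 13.4.** The Chief Investigator is responsible for "Ensuring that all SAEs are recorded in EDC and reported to the ExeCTU Trial Manager within 24 working hours / 1 working day"; the clock starts when the event becomes known. The sponsor reports to the ethics committee the SAEs that are related and unexpected.

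**Section 13.1.** Serious and non-serious events are to be recorded "within both groups and report them to the Research Ethics Committee to determine whether events are related to the treatments".

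**Section 13.2.** The SAE list reads "Serious adverse events (SAEs) including death, suicide attempt, self-harm, serious accident or violent incident" and continues with crisis referral and psychiatric admission. The AE list ends with "new instance of self-harm, new instance of suicidality". The adapted AE definition in Table 12 is limited to participants who have been administered the intervention.

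**The concern.** Four parts of one safety chapter give different answers to basic operational questions: which SAEs must be reported promptly, which go to the ethics committee, whether self-harm is serious, and whether a control participant can have an AE at all.

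The relatedness condition in 13.3 is the central problem. It places a causal judgement ahead of prompt reporting, although the form that documents this judgement is completed as part of reporting. The condition is also unlikely to act equally on the two arms. Under section 9.2, delayed-treatment participants receive the intervention only after the first group has completed its six weeks. Until then, an SAE in that arm cannot be attributed to treatment.

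What is at stake is a consistent safety picture. Section 12.7 would discontinue the trial on cumulative evidence of harm, and section 14.3.2 intends suicidality to be monitored by arm. Both are easier to interpret if the same event follows the same path in either arm.

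**Working it through.** The plan gives no figure to reproduce, so the check is a comparison of the text.

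**Step 1. Set the rules side by side.**

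| Question | 13.1 | 13.3 | 13.4 |
|---|---|---|---|
| SAEs to be reported promptly | no clock given | related to trial or treatment | all |
| Unrelated SAEs | recorded, both groups | monitored, no deadline | same clock as related |
| Sent to the ethics committee | serious and non-serious events, to determine relatedness | related and unexpected SAEs | related and unexpected SAEs |

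**Step 2. Trace one event.** Take a serious accident, which 13.2 lists as an SAE, in a delayed-treatment participant before the intervention is received. Suppose it is thought unrelated.

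- Under 13.3 it is monitored and entered at an assessment. It has no deadline and does not go to the ethics committee.
- Under 13.4 it is recorded and reaches the Trial Manager within one working day of awareness. It does not go to the ethics committee.
- Under 13.1 it is recorded and goes to the ethics committee, which is to help determine relatedness.

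One event has three different paths.

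**Step 3. Test the condition against the form.** If only related SAEs were recorded and reported, the not-related grade on the SAE form would never be used. The form therefore expects unrelated SAEs. It fits 13.4 and does not fit the opening sentence of 13.3.

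**Step 4. Direction by arm.** The 13.3 condition is met if an event is related to the trial or to the treatment. In the intervention arm either branch can be met. In the delayed-treatment arm before crossover only the trial branch can. The condition is therefore harder to meet in that arm during roughly the first six of the twelve weeks. This gives a direction. The size would need an SAE rate and the share of events judged related, and the protocol states neither.

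**Step 5. Classification.** Self-harm is on the SAE list in 13.2 without a qualifier, on the AE list in 13.2 as a new instance, and under the life-threatening category of the form in 13.3. Section 13.2 does not say what separates the first two. The AE definition in Table 12 excludes untreated participants, whereas 13.1 covers both groups.

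**Step 6. Deadline.** Both 13.3 and 13.4 equate one working day with 24 working hours. The unit is ambiguous, but the two sections agree with each other.

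**The case against.** The strongest defence reads 13.3 as a whole. Its first sentence describes an expedited pathway and its second paragraph describes routine capture, so nothing is lost.

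Much of this stands. A reader might infer from the first sentence that control-arm SAEs go unreported, or that almost none would be recorded before crossover. The documents do not support that. The second paragraph of 13.3 enters any adverse event into the database without restriction by arm. Section 13.1 names both groups, 13.4 covers all SAEs, 13.5 covers all deaths whatever the cause, and 14.3.2 logs suicide-risk answers automatically. The condition also includes trial-related events, so a control participant can meet it, and unrelated events in the intervention arm are filtered too. Nor does 12.7 specify a between-arm SAE comparison.

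Expected SAE counts per arm would rest wholly on an assumed risk. Turning 24 working hours into several days would need a length of working day that the protocol never states. Neither figure belongs in the argument.

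On self-harm, SAEs are ordinarily a subset of AEs, the AE list is illustrative, and Table 12 defines life-threatening. A partial criterion therefore exists, but the SAE list in 13.2 does not apply it.

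The safety flow chart (Figure 2) cannot be seen in the text available, and 13.4 refers to a Trial Monitoring Plan. Either may clarify routing in practice.

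The defence does not remove the conflict. Even read as two pathways, 13.3 gives an unrelated SAE no deadline where 13.4 gives one working day, and 13.1 still describes a different ethics-committee rule.

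**Conclusion.** The contradiction holds, as one of timing, route and class. There are four substantive conflicts:

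- the scope of prompt SAE reporting (13.3 against 13.4);
- what goes to the ethics committee (13.1 against 13.3 and 13.4);
- the class of self-harm (within 13.2, and on the form in 13.3);
- the population covered by the AE definition (13.2 against 13.1).

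The ambiguous deadline unit is a minor addition.

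Events are captured in both arms. The possible difference by arm is in prompt reporting and rests on one assumption: that staff apply the relatedness condition in 13.3 and more often judge pre-crossover events in the delayed-treatment arm unrelated. Its size cannot be derived from the protocol. The correction is worth making because it concerns a stated safety rule and costs little.

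**What to change.** Reconcile sections 13.1 to 13.4 together, because changing one sentence would leave the others in conflict.

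- **13.3, first paragraph:** remove the relatedness condition from recording and prompt reporting, so that all SAEs in both arms follow 13.4. Relatedness is then judged on the form after the event has been recorded.
- **13.3, second paragraph:** take unrelated SAEs out of the list of events that are only monitored.
- **Ethics committee:** state one rule for what is sent and when, and align 13.1, 13.3 and 13.4 with it.
- **13.2, Table 12:** make the adapted AE definition apply to participants in both arms.
- **13.2, self-harm:** state one seriousness criterion that decides between SAE and AE, and use the same criterion on the form.
- **Deadline:** give it in one unit in both 13.3 and 13.4.
- **Figure 2 and the Trial Monitoring Plan:** check that they match the revised text.

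The cost is protocol wording and a few more expedited forms. No change to the design, sample size or assessment schedule is needed.

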7. PARTICIPANT INCLUSION/EXCLUSION CRITERIA

Table 8 Inclusion/Exclusion criteria

Inclusion	Exclusion
Aged 16 or over.	AGED 16<
PHQ9=<9; GAD7=<9	PHQ9>9; GAD7>9
Suicide risk: PHQ9; Q9=<1 and R2=No and R3=	Suicide risk: PHQ9; Q9>1 and R2=Yes and/or R3
No	=Yes
Resident in UK	
Student at the University of Exeter	Past history of psychosis, mania,
	substance/alcohol dependence

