12.7 Interim analysis and criteria for the premature termination of the trial

No interim analyses are planned. In order to detect potential harms the study will monitor potential adverse effects. Adverse and serious adverse effects will result in trial discontinuation if there is cumulative evidence that the intervention may cause harm.

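### The protocol defines a symptom-related adverse event in three incompatible ways, and its one score rule fits poorly with entry at 9 or less on PHQ-9 and GAD-7

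*Protocol*

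**What the plan says.** Four parts of the Protocol bear on whether worsening depression or anxiety is an adverse event (AE).

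- **Section 13.2, list item ii.** "Adverse Events (AE) may include significant worsening symptoms of anxiety, worsening symptoms of depression". The rule requires "movement from 'mild' to 'severe' or 'moderate' to 'severe' levels of symptoms on GAD7 or PHQ9" and, jointly, "a change of ≥4 points on GAD7 or ≥6 points on PHQ9 from baseline assessment to 6 weeks assessment" or the same change between 6 and 12 weeks. New self-harm and new suicidality also count.
- **Section 13.2, Table 12, adapted definition.** "Any deterioration in mental state or behaviour in a participant to whom the intervention has been administered", whether or not it is related to the intervention.
- **Section 13.3.** "Symptoms of depression or anxiety will not be defined as adverse events unless suicidal ideation, plans or an attempt has been made". The serious-event form in the same section nevertheless offers the onset of a new Axis I disorder as an example under disability or incapacity.
- **Section 13.1.** Serious and non-serious events are to be recorded in both arms.

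Entry requires "PHQ9=<9; GAD7=<9" (section 7, Table 8). The discontinuation rule in section 12.7 draws on these data: "Adverse and serious adverse effects will result in trial discontinuation if there is cumulative evidence that the intervention may cause harm".

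**The concern.** Staff who follow different parts of the same protocol would produce different AE counts for the same participants. An analysis plan cannot fully repair that later, because it affects what is recorded as an AE in the first place.

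The score rule adds a second problem. This is a prevention study in students who are well at entry, so the natural harm signal is a new rise to clinical-level symptoms. A rule built on moves from mild or moderate to severe is aimed at people who start higher. No interim analysis is planned, so the judgement about cumulative harm in section 12.7 leans on the AE data, and gaps there matter more than they would in a trial with scheduled comparisons.

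**Working it through.** The protocol gives no event rate or power figure on this point, so there is none to reproduce.

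**Step 1. Apply each rule to the same change between baseline and 6 weeks, with no suicidality.** The protocol does not define the bands. Assumed here: mild from 5; severe from 20 on PHQ-9 and from 15 on GAD-7.

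| PHQ-9 change | 13.2 list | Table 12 | 13.3 |
|---|---|---|---|
| 9 to 21 (+12) | AE | AE if given the intervention; not for an untreated control | Not an AE |
| 4 to 19 (+15) | Not met | AE if given the intervention; not for an untreated control | Not an AE |

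The second participant ends above the PHQ-9 cut-off of 10 that section 10.2, Table 10 cites for major depression.

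**Step 2. Rise needed from an eligible score.** Minimum rise = lower limit of severe minus starting score.

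- PHQ-9 from 9: 20 − 9 = 11; from 5: 20 − 5 = 15. If severe means above 20, the flag used in section 13.1, these become 12 and 16.
- GAD-7 from 9: 15 − 9 = 6; from 5: 15 − 5 = 10.
- From 0–4: the starting band is below mild, so no later score qualifies within one interval.

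The stated 6-point and 4-point thresholds therefore add nothing for anyone starting at 9 or less.

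**Step 3. Share of score pairs accepted.** Count the integer pairs with a start of 0–9 and a rise that meets the protocol's own threshold.

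- PHQ-9 (maximum 27, rise of 6 or more): the sum over b = 0 to 9 of (22 − b) = 220 − 45 = 175. Accepted: 5 starts (5–9) × 8 end scores (20–27) = 40. 40/175 = 23%.
- GAD-7 (maximum 21, rise of 4 or more): the sum of (18 − b) = 180 − 45 = 135. Accepted: 5 × 7 end scores (15–21) = 35. 35/135 = 26%.

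Sensitivity to the bands:

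| Scale | Mild from | Severe from | Accepted |
|---|---|---|---|
| PHQ-9 | 5 | 21 | 35/175 = 20% |
| PHQ-9 | 0 | 20 | 80/175 = 46% |
| PHQ-9 | 5 | 15 | 65/175 = 37% |
| PHQ-9 | 0 | 15 | 130/175 = 74% |
| GAD-7 | 5 | 16 | 30/135 = 22% |
| GAD-7 | 0 | 15 | 70/135 = 52% |

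**Step 4. An illustration in participants.** Score pairs are not equally likely, so a simulation shows the scale of the loss. Assumed: 60 per arm (120 planned, 1:1), starting scores uniform on 0–9, mean rise 3, SD of change 3 or 5, and the Step 1 bands. Results are expected numbers per 60.

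| Scale | Meet the point threshold | Also meet the band rule |
|---|---|---|
| PHQ-9 | 12.2 (SD 3); 18.5 (SD 5) | 0.07; 1.02 |
| GAD-7 | 26.0 (SD 3); 27.5 (SD 5) | 2.63; 5.72 |

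**Step 5. Time windows.** Change is judged from baseline to 6 weeks and from 6 to 12 weeks, never from baseline to 12 weeks. Take PHQ-9 scores of 9, 15 and 20. The first step is +6 but ends below severe; the second ends at severe but is only +5. The total of 20 − 9 = 11 is never tested. If severe began at 15, the first step would qualify.

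**The case against.** The other side has real points, and several limit what can be concluded.

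- **The list is open-ended.** Item ii in section 13.2 says what AEs may include, and Table 12 is broad. That is true, but the score rule is the only operational one, and the exclusion in section 13.3 is categorical.
- **Other harm is captured.** A reader might infer that the trial would report almost no harm whatever happened. The documents do not support that. Section 13.2 counts death, suicide attempt, self-harm, crisis referral and psychiatric admission as serious events, and new self-harm or suicidality as AEs. Section 14.1.2 logs PHQ-9 above 20 and any positive item 9. Section 13.3 monitors serious deterioration, although it does not define it. Even the score rule would register something: under the Step 4 assumptions, a mean GAD-7 rise of 6 gives about 10–12 AEs per 60.
- **Controls.** A reader might infer that untreated controls are left out of safety recording. Only the Table 12 wording does that. Section 13.1 covers both arms, Table 9 in section 8.11 schedules AE assessment without restriction by arm, and section 14.3.2 monitors suicidality across arms. This is a contradiction to settle, not an omission.
- **Point thresholds.** A reader might infer that they never bind. They are redundant only from a start of 9 or less; between 6 and 12 weeks they can bind, as the step from 15 to 20 shows.
- **Moderate to severe.** It is tempting to call this move impossible from baseline. The ceiling of 9 is an eligibility criterion applied at screening, and section 10.3 measures both scales again at baseline, so a few participants may start higher. The move also has a clear role after week 6.
- **Unseen plans.** Section 12.3 defers detail to an analysis plan and section 13.4 refers to a Trial Monitoring Plan. These may specify tables, but they do not remove conflicting definitions from the protocol. The scores are collected in both arms, so deterioration stays recoverable, which is why the repair is cheap.

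**Conclusion.** The point holds. Sections 13.1, 13.2 (list and Table 12) and 13.3 cannot all be followed, and this rests on the text alone. For worsening without suicidality, section 13.3 gives no AE, the section 13.2 list captures it rarely, and Table 12 counts it without a threshold but only in those given the intervention.

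The size of the shortfall depends on bands that the protocol does not state. With severe at 20 or 21 on PHQ-9 and at 15 or 16 on GAD-7, and mild starting anywhere from 0 to 5, the score rule accepts 20–46% and 22–52% of the score pairs that meet the protocol's own thresholds. If PHQ-9 severe began at 15, the range would be 37–74%, so the statement that most deterioration is missed depends on the bands. The simulated counts rest further on assumed distributions.

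The consequence is weaker AE evidence for the decision in section 12.7, not its absence. The reconciliation should be made, because the same participant can be counted in conflicting ways.

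**What to change.** 1. Reconcile section 13.1, the section 13.2 list, Table 12 and section 13.3 into one AE definition. State the PHQ-9 and GAD-7 bands and apply the definition to all randomised participants in both arms. Which definition is kept is for the investigators; the new-disorder example on the serious-event form should agree with it.
2. Whichever is kept, add one descriptive table by arm:
   - number and proportion (95% CI) whose score rises by the protocol's own 6 points (PHQ-9) or 4 points (GAD-7), from baseline to 6 weeks and from baseline to 12 weeks, regardless of starting band;
   - number newly at or above the PHQ-9 cut-off of 10 cited in section 10.2.
3. Read that table as treated versus untreated only at 6 weeks, because section 9.2 gives controls the intervention after that period.

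The cost is wording in section 13 and one table, with no new assessments. The downside is that more events will be listed, some of them natural fluctuation; the control column puts those in context.

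### Non-suicidal worsening of depression or anxiety can be an adverse event under section 13.2 but not under 13.3, and the protocol does not say which rule applies

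*Protocol*

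**What the plan says.** Three places in the protocol define when a change in depression or anxiety symptoms is an AE.

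- **Section 13.2(ii)** treats worsening as an AE: "Adverse Events (AE) may include significant worsening symptoms of anxiety, worsening symptoms of depression, as operationalized by a reliable deterioration of movement" from mild or moderate to severe, together with "a change of ≥4 points on GAD7 or ≥6 points on PHQ9". The change is measured from baseline to week 6 or from week 6 to week 12. New self-harm and new suicidality are separate items in the same list.
- **Table 12 in section 13.2** gives a general definition with no threshold: "Adapted: Any deterioration in mental state or behaviour in a participant to whom the intervention has been administered".
- **Section 13.3** takes symptoms out of the AE definition, with one exception: "Symptoms of depression or anxiety will not be defined as adverse events unless suicidal ideation, plans or an attempt has been made".

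Section 13.3 also lists serious deterioration as something to monitor alongside AEs, without defining it. On the SAE form, "onset of new Axis I disorder" is given as an example under persistent or significant disability or incapacity. It does not appear in the SAE list in 13.2(i).

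**The concern.** In 13.2(ii), suicidality is not a condition of the symptom item, because it has its own entry. In 13.3 it is the only route by which depression or anxiety symptoms become an AE. The two rules disagree on every participant who meets the 13.2(ii) score criteria without suicidality, and the protocol gives no order of precedence.

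Several parts of the protocol rely on the classification. Section 13.1 has serious and non-serious events in both groups recorded and sent to the ethics committee. Section 13.4 requires AEs to be recorded as the protocol specifies and verified against it. Section 12.7 bases early termination on accumulating adverse effects. The intervention is meant to prevent mental health difficulties, so worsening mood and anxiety are central to its harm profile. An AE table by arm cannot be reproduced if the reader does not know which paragraph produced it.

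**Working it through.** The protocol states no expected event rate and no figure for this point, so there is nothing to reproduce. The check is to apply each rule to the same cases.

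**Inputs**
- Entry limit: PHQ-9 and GAD-7 of 9 or less at screening (section 7, Table 8).
- Minimum change: 6 points on PHQ-9 or 4 on GAD-7, plus a move to severe (section 13.2(ii)).
- Severe range: the protocol gives no bands. Section 13.1 uses PHQ-9 above 20 as its example of severe distress. I take 9 as mild and 21 as severe; both are assumptions.

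**Cases**

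| Case | 13.2(ii) | Table 12 (adapted) | 13.3 |
|---|---|---|---|
| PHQ-9 from 9 to 21, no suicidality | AE | AE | not an AE |
| PHQ-9 from 9 to 21, with new suicidal ideation | AE | AE | AE |
| PHQ-9 from 5 to 9, no suicidality | not an AE | AE if read literally | not an AE |

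In the first row the change is 21 − 9 = 12 points, which exceeds 6, and the move is from mild to severe. In the third row the change is 9 − 5 = 4 points, below 6, and the score does not reach severe.

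The first row is the direct contradiction between 13.2(ii) and 13.3. The second row shows that the rules agree once suicidality is present, so the disagreement is confined to non-suicidal worsening. The third row shows that the Table 12 wording is wider than either rule.

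**Size**

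From baseline, the rise needed is the lowest severe score minus the starting score. With severe taken as 21:
- from 9: 21 − 9 = 12 points, twice the 6-point minimum;
- from 5: 21 − 5 = 16 points.

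Few participants who enter well are likely to move that far in six weeks, so the PHQ-9 gap between 13.2(ii) and 13.3 is probably small. It is not zero. From week 6 to week 12 the starting score is no longer limited by the entry criterion; from 15, for example, 21 − 15 = 6 points is enough, if 15 counts as moderate. The same structure applies to the GAD-7, but its bands are not stated either and I have not put a size on it. The protocol gives no score distribution or event rate from which to compute a count.

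**The case against.** The best defence is that 13.3 refers to the mere presence of symptoms, which are common, while 13.2(ii) refers to reliable worsening; and that 13.2 says only that AEs may include such worsening. That would remove the conflict, but 13.3 does not draw the distinction. It names serious deterioration as a separate monitored item without calling it an AE. If 13.3 governed, the score thresholds in 13.2(ii) would have almost no function, because new suicidality is already listed there in its own right.

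A second defence is that symptom harm is not lost whatever it is called. Section 13.1 makes the questionnaires the main indicators of harm, 14.1.2 logs every PHQ-9 above 20 and informs the Trial Manager and chief investigator, and 12.6.2 reports the scores by arm. This stands: it limits the damage and means any rule can be applied to stored scores. It does not say which cases enter the AE table.

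Three stronger readings are tempting but not supported:
- **That the same case is also an SAE.** The form names a new Axis I disorder as an example of disability or incapacity. A rise in score is not a diagnosis, and the outcome set contains no diagnostic interview. An SAE is also a kind of AE, so the form does not by itself contradict 13.2.
- **That Table 12 makes every one-point rise an AE.** The table is presented as adapted in light of 13.2(i) and (ii), and the protocol nowhere applies it to single points. The fair criticism is only that its wording is broader than the rule it sits beside.
- **That the 12.7 decision follows mechanically from the count, or that blinded and unblinded staff would classify cases differently.** Section 12.7 has no numerical trigger and calls for a judgement. Nothing in the text supports the claim about staff.

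**Conclusion.** The contradiction between 13.2(ii) and 13.3 is real, and the adapted AE entry in Table 12 adds a third, wider wording. A non-suicidal deterioration that meets the score rule is one AE or none, depending on the paragraph read. The AE count by arm, ethics reporting and the evidence feeding the 12.7 judgement inherit that ambiguity.

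The worked example rests on treating PHQ-9 9 as mild and 21 as severe. The effect on the trial's counts cannot be computed from the document. For the PHQ-9 it is probably small between 13.2(ii) and 13.3; for the GAD-7 it is unquantified. This should be corrected because it makes the harm definition unreproducible, not because a large shift in counts has been shown.

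**What to change.** Reconcile 13.2(ii), the adapted AE entry in Table 12 and the 13.3 sentence into one symptom-change rule. Which rule to adopt is for the trial team to decide. Then:

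1. State the rule once, with its severity bands if it uses them, and have the other two passages refer to it.
2. Derive it by program from the PHQ-9 and GAD-7 scores already held in the EDC system, identically in both arms. The wording should cover both arms explicitly, since Table 12 speaks of participants who have received the intervention while 13.1 records events in both groups.
3. As a minor addition, say how "onset of new Axis I disorder" on the SAE form relates to the rule, leaving the seriousness criteria in Table 12 and on the form in place.

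The cost is a few wording changes and one derived variable. No new data are needed.
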